## **9 Statistical Analysis**

### **9.1 General Considerations**

In general, continuous variables will be summarized as n, mean, standard deviation, median, minimum, and maximum. Categorical variables will be summarized as the number and percentage of patients in each category.

Summary tables will present data for both treatment groups and overall, where appropriate. Data listings will include all data collected on the case report forms (CRFs), as well as any derived variables (study day, age, etc.). Data collected on patients who are screen failures will not be included in any summary tables, listings, or analyses.

For each parameter, baseline is defined as the value reported prior to the study procedure: PAE or RALRP for the PAE group (specified below for each outcome) and RALRP for the Control group. If multiple values were collected prior to the procedure, the value closest to the date/time of the initiation of the procedure will be used as baseline. This may include values collected earlier in the day on the date of procedure.

Any outliers detected during the review of the data will be investigated. If needed the data will be queried and corrected in the database prior to database lock and the generation of the final tables and listings.

All analyses will be performed on a locked database after all patients have completed Visit 7, died or been lost to follow up. Analyses will be performed using SAS® (Statistical Analysis System), version 9.1 or higher.

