### **2.2 Secondary Objectives**

The key secondary objectives are to assess the outcomes listed below and to compare the results for patients who receive PAE and those that do not:

1. Change in hemoglobin on RALRP post operative day (POD) 1 compared to baseline
2. Change in hematocrit on RALRP post operative day (POD) 1 compared to baseline
3. Change in prostate volume between baseline and Visit 3 (6 weeks  $\pm$  2 weeks post PAE) as determined by MRI in patients who receive PAE
4. Blood transfusion requirements during RALRP
5. RALRP duration in minutes
6. Length of hospital stay for RALRP
7. Presence or absence of a complete surgical margin around the entire tumor as determined by histopathology examination post RALRP
8. Biochemical recurrence of prostate cancer as determined by PSA levels post RALRP at 1 year follow up
9. Return to continence post RALRP as assessed by the pad weight test.
10. RALRP related adverse events
11. Erectile function compared to baseline as assessed by the IIEF post RALRP at 1 year follow up.

Additional secondary objectives are to assess outcomes listed below for patients that receive PAE:

12. Change in PSA between baseline and Visit 3 (6 weeks  $\pm$  2 weeks post PAE)
13. PAE related adverse events
14. Histologic changes in the prostate after PAE

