## 4 Study Design

This is a phase 2, prospective, non-randomized, matched-pair, single center study designed to evaluate the safety and efficacy of PAE using Embosphere Microspheres as a pre-operative tool in patients with biopsy-proven adenocarcinoma of the prostate with localized disease. A total of 10 patients with biopsy-proven prostate carcinoma with localized disease will be enrolled in the study to receive pre-prostatectomy PAE, and matched with 10 controls who will not receive pre-prostatectomy PAE, in order to evaluate the study objectives. Patient recruitment is anticipated to take approximately 2 years. Duration of participation is expected to be approximately 15 months from time of enrollment, including a minimum of 12 months follow up. This study will have a stop limit for re-evaluation after two patients with serious adverse events attributed to confirmed or suspected non-target embolization have been identified.

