### **5.6 Visit 5 (12 days +/- 7 days)**

Patients in the PAE group and the Control group will have the following:

- Physical exam including vital signs, weight, and genitourinary evaluation
- Blood and urine laboratory evaluations as at baseline
- Concomitant medications
- Adverse events
- Urinary catheter removal

Cystoscopy and proctoscopy will be performed: 1) if medically indicated, especially if there is pain out of proportion to that which is expected, 2) in all cases of bleeding per rectum, and 3) in cases of hematuria beyond that which is reasonably expected following prostatectomy.**5.7 Visits 6, 7, 8, 9 (3, 6, 9, and 12 months ± 2 weeks for each visit post RALRP)**

Patients in the PAE group will have the following assessments performed:

- Physical exam including vital signs, weight, and genitourinary evaluation
- Prostate Specific Antigen (PSA)
- Expanded Prostate Cancer Index Composite (EPIC) questionnaire
- International Index of Erectile Function (IIEF) questionnaire
- Pad weight test
- Concomitant medications
- Adverse events

Cystoscopy and proctoscopy will be performed: 1) if medically indicated, especially if there is pain out of proportion to that which is expected, 2) in all cases of bleeding per rectum, and 3) in cases of hematuria beyond that which is reasonably expected following prostatectomy.

Patients in the Control group will have the following assessments performed:

- Physical exam including vital signs, weight, and genitourinary evaluation
- Prostate Specific Antigen (PSA)
- Expanded Prostate Cancer Index Composite (EPIC) questionnaire
- International Index of Erectile Function (IIEF) questionnaire
- Pad weight test
- Concomitant medications
- Adverse events

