## **7.2 Adverse Event Reporting**

The Investigators are responsible for monitoring the safety of patients who have been enrolled in this study. All AEs considered to be related to study treatment will be followed until the event resolves or has reached a final outcome. Adverse events will be evaluated for severity using NCI CTCAE (Common Toxicity Criteria for Adverse Events) where applicable.

Investigators are required to document all AEs occurring during the study commencing with the date of PAE treatment for patients in the PAE group, and from date of RALRP for the Control group, and including the protocol defined post-treatment follow-up period (21 CFR §312.64[b]), which is defined as 12 months post day of treatment, on the designated CRF pages. AEs that occur following the signature of informed consent but prior to treatment will not be captured. SAEs that occur following the signature of the informed consent but prior to treatment will not be reported.

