#### ***9.5.2.7 Biochemical Recurrence of Prostate Cancer***

An analysis of the presence or absence of biochemical recurrence of prostate cancer as determined by PSA levels post RALRP at one year follow-up (Visit 9) will be performed. Each patient will be classified as having biochemical recurrence or not, and proportions will be summarized, including 95% confidence intervals. Treatments will be compared using an exact binomial sign test.

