#### ***9.5.2.8 Return to Continence***

An analysis of return to continence post RALRP will be performed using the pad weight test. Patients will be classified as being continent if the weight of the pad increase is insignificant; mild incontinence if the weight of pad increases by <400 grams over 24 hours and as incontinent if the weight of the pad increases by  $\geq 400$  grams over 24 hours. The pad weight test will be performed at the following post-RALRP timepoints: 12 days (if urinary catheter is removed), 3 months, 6 months, 9 months, and 12 months. The proportion of continent patients will be calculated for each treatment group at each timepoint. Treatments will be compared using an exact binomial sign test.

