#### ***9.5.2.9 Erectile Function***

The IIEF is a commonly used, validated instrument that consists of 15 items. Five subscales are calculated as follows:

- Erectile Function (items 1, 2, 3, 4, 5, 15)
- Orgasmic Function (items 9, 10)

- Sexual Desire (items 11, 12)
- Intercourse Satisfaction (items 6, 7, 8)
- Overall Satisfaction (items 13, 14)

Each subscale will be summarized separately for both treatment groups for the baseline (defined as pre-PAE for the PAE group and pre-RALRP for the Control group), 3 month, 6 month, 9 month, and 12 month timepoints, including change from baseline. Treatment means for the change from baseline will be compared using a matched pairs t-test.

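### Section 9.1 allows the database to be locked for all analyses after the 6-month visit (Visit 7), although recurrence is analysed at 12 months and continence and IIEF run to 12 months

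*Combined protocol and SAP*

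**What the plan says.** Section 9.1 gives one rule for the timing of the analysis: "All analyses will be performed on a locked database after all patients have completed Visit 7, died or been lost to follow up". The preceding paragraph of that section places data correction before database lock and the production of the final tables, so the lock in question is the one that feeds the final outputs.

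The heading of section 5.7 fixes the visit calendar: "Visits 6, 7, 8, 9 (3, 6, 9, and 12 months ± 2 weeks for each visit post RALRP". Appendices A1 and A2 use the same visit numbers and months.

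The analyses and objectives that reach beyond month 6 are:

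- Secondary objective 8 (section 2.2): "Biochemical recurrence of prostate cancer as determined by PSA levels post RALRP at 1 year follow up". Objective 11 in the same list sets erectile function at 1 year as well.
- Section 9.5.2.7, recurrence: "as determined by PSA levels post RALRP at one year follow-up (Visit 9) will be performed".
- Section 9.5.2.8, continence by pad weight: "12 days (if urinary catheter is removed), 3 months, 6 months, 9 months, and 12 months".
- Section 9.5.2.9, the IIEF subscales, after baseline: "3 month, 6 month, 9 month, and 12 month timepoints, including change from baseline".

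Two further statements concern follow-up. Section 4 describes participation "including a minimum of 12 months follow up", and section 7.2 sets a follow-up period for adverse events, "which is defined as 12 months post day of treatment".

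**The concern.** A lock rule should say when the data are complete enough for the planned analyses. This one is met two visits too early: Visits 8 and 9 may still be outstanding for some patients when the condition is satisfied. It covers all analyses, and nothing elsewhere in the statistical section provides a second lock, an interim cut or an update.

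If the lock were taken at or soon after the stated point, every patient operated on less than about 6 months before the last one would have no 12-month assessment. The shortfall would probably not be even between groups. Section 4.2 selects controls only once the 10 PAE patients have been identified, so the last operations are likely to be in controls. The planned tests are paired (matched-pairs t-test, exact sign test), so a missing control also takes its PAE partner out of the comparison. Adverse events late in follow-up would be under-counted for the same patients.

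The wording also leaves the lock date open anywhere from month 6 onwards in a non-randomised study with no blinding described. That is avoidable discretion over which 1-year data enter the analysis.

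**Working it through.** The plan gives no figure to reproduce here: section 9.2 says that no formal sample size calculation was done, and no significance level is stated. The check compares dates, followed by an illustration of size.

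**1. Timing, from the documents alone.** Visits 6, 7, 8, 9 correspond to months 3, 6, 9, 12 after RALRP.

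| Analysis | Last timepoint | Complete at the Visit 7 trigger? |
|---|---|---|
| EBL and other perioperative outcomes | Visit 4 or shortly after | Yes |
| Continence, IIEF at 3 and 6 months | Visits 6, 7 | Yes |
| Continence, IIEF at 9 and 12 months | Visits 8, 9 | Not assured |
| Biochemical recurrence | Visit 9 only | Not assured |

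Gap between trigger and last timepoint: 12 − 6 = 6 months. The ±2-week windows at both ends make it about 5.1 to 6.9 months.

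**2. Controls with data at the earliest lock (accrual assumed).** Place 10 control operations at times i·S/9, i = 0,…,9, over a span of S months, with the last control being the last patient. A control has 12-month data if operated on at least 6 months before the last, and 9-month data if at least 3 months before.

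| S (months) | 12-month data | 12-month data, gap of 7 to 5 months (windows) | 9-month data |
|---|---|---|---|
| 6 | 1 of 10 | 0–2 | 5 of 10 |
| 12 | 5 of 10 | 4–6 | 7 of 10 |
| 18 | 7 of 10 | 6–7 | 8 of 10 |

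**3. PAE patients.** Assume total recruitment of 24 months (section 4 says about 2 years), with PAE patients identified evenly over 24 − S months before the first control. Their wait from baseline to RALRP is 8–16 weeks (0–4 weeks to PAE plus 10 ± 2 weeks). The control wait is 0–12 weeks (section 5.1). At the nominal 6-month gap, 0–2 PAE patients lack 12-month data at S = 6, and none at S = 12 or 18. A 7-month gap raises the upper figure at S = 6 to 3. Taking the control wait as 10–14 weeks, from Appendix A2, makes the nominal range 0–1.

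**4. A different accrual assumption.** With all 20 operations evenly spaced over 24 months, 5 of 20 patients lack Visit 9 and 3 lack Visit 8 at the trigger. For spans of 12, 18 and 30 months, 10, 7 and 4 of 20 lack Visit 9.

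**5. Effect on precision.**

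- Upper exact 95% limit with 0 recurrences among n patients, 1 − 0.025^(1/n): n = 10, 30.8%; n = 7, 41.0%; n = 5, 52.2%.
- 95% CI half-width for a paired IIEF difference, t(0.975, n−1)/√n, in SDs of the differences: 2.262/√10 = 0.72; 2.447/√7 = 0.92; 2.776/√5 = 1.24.
- Smallest two-sided exact sign-test p with m discordant pairs, 2 × 0.5^m: m = 10, 0.002; m = 6, 0.031; m = 5, 0.0625.

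**The case against.** The strongest reply is that 'after' sets a floor. A lock taken after the last Visit 9 complies with section 9.1, and the specific provisions for 1-year outcomes can be carried out only if the team waits. On that reading the visit number is a slip in a general paragraph and nobody intends to analyse early. The text does permit waiting, and a slip is a likely explanation. But a pre-specified lock rule should not depend on the reader setting its wording aside, and no other passage supplies a later date.

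Two of the supporting passages are weaker than the rest. The 12-month minimum follow-up and the adverse-event period govern how long patients are observed; they do not say when the database closes. The adverse-event period also runs from PAE in the PAE group, so with RALRP 8–12 weeks later it ends about 9 to 10 months after RALRP in that group and at 12 months in controls. Both points stand. Both ends are still beyond month 6, and the direct conflict with section 2.2 and sections 9.5.2.7 to 9.5.2.9 does not need these passages.

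The size is driven by assumptions, and 1 to 7 of 10 controls is a wide range. That is correct; the counts show only that the loss could be material.

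The sign test is also weak with all 10 pairs. It needs at least 6 discordant pairs to go below 0.05. If recurrence were equally likely in both groups and independent within pairs, at 10%, 20% or 30%, a pair would be discordant with probability 2p(1−p) = 0.18, 0.32 or 0.42, and the chance of 6 or more among 10 would be 0.4%, 6% or 20%. So for recurrence the early lock costs mainly completeness and interval width, and little in test power.

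Finally, the primary outcome is untouched and the study is a proof of concept. That limits the severity.

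**Conclusion.** The concern holds. The lock condition in section 9.1 can be met 6 months before the last planned timepoint, and it conflicts with objectives 8 and 11 and with sections 9.5.2.7, 9.5.2.8 and 9.5.2.9. This conclusion needs no assumption: it follows from the visit calendar and the absence of any later lock.

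The consequence is conditional. It arises only if the lock is taken at or near the earliest permitted date, and its extent depends on accrual. Under the even-spacing assumption, between 1 and 7 of 10 controls would have 12-month data, with few or no PAE patients missing. That the loss falls mainly on controls is an inference from the order of selection. The 0.05 level used to read the sign test is also an assumption.

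This should be fixed. It affects secondary outcomes and late adverse events, and leaves the primary comparison of blood loss intact.

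**What to change.** In section 9.1, replace Visit 7 with Visit 9 as the visit that every patient must have completed, unless dead or lost to follow-up, before the final lock.

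If an earlier readout is wanted, define it in the plan as a separate, named data cut limited to the perioperative outcomes: EBL, hemoglobin and hematocrit change, transfusion, operating time, length of stay and surgical margins. Hold recurrence, the 9- and 12-month continence and IIEF analyses, and the final adverse-event summaries for the Visit 9 lock.

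The text change is one visit number. No visits or procedures are added, because Visits 8 and 9 are already scheduled. The earliest permitted final lock moves about 6 months later (about 5.1 to 6.9 with the visit windows). After the change, no 1-year value would be missing because of the lock date; the limited information from 10 pairs remains.

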### **9.2 Sample Size Calculations**

This is a proof of concept study and therefore, formal sample size calculations were not performed. Ten patients will be assigned in a non-randomized sequential manner to the PAE treatment group. Ten patients will also be assigned as matched controls in a 1:1 ratio to PAE treated patients based on risk group as defined in section 4.2. This sample size will provide sufficient data to assess the preliminary safety and efficacy of PAE treatment prior to RALRP.

### **9.3 Analysis Populations**

All PAE patients who are treated with PAE and RALRP, and all Control patients who are treated with RALRP will be included in the Safety Population. This will be the population used for both safety and efficacy analyses.

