### 3.2 Exclusion Criteria

Patients meeting any of the following exclusion criteria may not be entered into the study:

1. Active urinary tract infection
2. History of life threatening allergy to iodinated contrast agents
3. Any known condition that limits catheter-based intervention or is a contraindication to embolization (eg shunt or adverse arterial anatomy)
4. Patient is unable to undergo MRI imaging
5. Cardiac condition including congestive heart failure or uncontrolled arrhythmia, uncontrolled diabetes mellitus, significant respiratory disease, or known immunosuppression which required hospitalization within the previous 6 months.
6. Baseline serum creatinine level  $> 1.8$  mg/dL
7. Baseline hemoglobin  $< 8.0$  g/dL
8. Active cystolithiasis or prostatitis
9. History of pelvic irradiation or radical pelvic surgery
10. Known major iliac arterial occlusive disease
11. Confirmed or suspected bladder cancer
12. Urethral strictures, bladder neck contracture, or other bladder or urethral pathology that could limit catheterization
13. Previous rectal surgery (other than hemorrhoidectomy) or history of rectal disease if the therapy or patient evaluation may potentially cause injury to sites of previous rectal surgery, e.g. if a transrectal probe is used
14. Previous pelvic irradiation or radical pelvic surgery
15. Previous prostate surgery, balloon dilatation, stent implantation, laser prostatectomy, hyperthermia, or any other invasive treatment to the prostate
16. Prior transurethral resection of the prostate or other invasive therapies
17. Coagulation disturbances not normalized by medical treatment
18. Acute urinary retention
19. Hypersensitivity to gelatin products
20. Any contraindication to embolization, including intolerance to vessel occlusion procedures, vascular anatomy/blood flow that precludes catheter placement or embolic agent injection, presence/likely onset of vasospasm, presence/likely onset of hemorrhage, severe atheromatous disease, feeding arteries smaller than distal branches, arteriovenous shunt, and collateral vessel pathways endangering normal territories during embolization or pelvic inflammatory disease

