### 4.2 Control Patients

A similar cohort of patients who undergo RALRP without PAE will be treated as a matched control group. The controls will be matched using a 1:1 ratio to PAE treated patients based on AUA risk group. Risk stratification will be as follows, according to AUA guidelines:

- Low risk: Stage T1c to T2a tumors, AND PSA  $\leq 10$ ng/mL, AND Gleason score  $\leq 6$

- Intermediate risk: Stage T2b tumors, OR PSA > 10ng/mL but ≤ 20ng/mL, OR Gleason score 7
- High risk: Stage T2c or higher tumors, OR PSA > 20ng/mL, OR Gleason score 8-10

Control patients will be selected after 10 patients for the PAE arm have been identified, such that the first potential control patient who matches the risk score of a PAE patient and agrees to participate in the study is matched to the appropriate member of the PAE arm. Once a match is identified, additional matches for a single PAE patient will not be sought. Because we are matching PAE and control patients based on AUA risk score only, we do not anticipate difficulty in finding a matched control for every PAE patient.

Control patients will sign written informed consent before any study-specific assessments are performed. Patients will complete EPIC and IIEF questionnaires within 12 weeks prior to RALRP, and will undergo MRI as a baseline study. Oncologic and functional outcomes will be evaluated by assessing PSA, EPIC, and IIEF at months 3, 6, 9, and 12 post RALRP, and then annually per standard follow-up protocol for the treating institution.

Safety will be evaluated for PAE patients throughout the study treatment and assessment periods by assessing adverse events, concomitant medications, changes in laboratory values, and findings on physical examination. Safety will be evaluated for Control patients during RALRP and the follow up period by assessing adverse events and concomitant medications.

The patients in both groups will continue to be followed post RALRP according to standard follow up protocol for the treating institution.

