## Appendix B2: Study Flowchart for Control Patients

## Appendix C: Technical Protocol for Prostate Artery Embolization

- Administer prophylactic IV antibiotics, based on institution standard of care. Choice of antibiotic and sedation will be at the discretion of the interventional radiologist.
- Prior to embolization, insert a Foley catheter into patient's bladder and fill it with a mixture of 50% contrast agent and 50% saline. This will provide a visual landmark during angiography.
- Local anesthesia should be administered for a trans femoral approach on the side with the best arterial pulse.
- Conduct pelvic angiography with a 5Fr catheter to evaluate aortoiliac vessels and prostate arteries during the arterial and late phases.
- Observe closely for vascular conditions and blood flow that might preclude catheter placement or embolic injection, including severe atheromatous disease, arteriovenous shunt, or presence of feeding arteries that are too small to accept the microspheres. If these conditions are present and a viable feeding artery without these problems cannot be identified, embolization will be conducted on the contralateral side of the prostate. If these conditions are present on both sides of the prostate, do not embolize.
- If appropriate, anastomoses to non-targeted vessels and/or endangering collateral vessel pathways will be closed off with a larger size of embolic particles or embolic coils chosen to be appropriate to the size of the anastomosis or collateral vessel. If anastomoses or endangering collateral vessels cannot be closed off, the embolization will be performed only on the contralateral side of the prostate, if it is not affected by the condition. If anastomosis or endangering collateral vessels affect both sides of the prostate, no embolization will be performed.
- If vasospasm occurs, follow institution standard of care, which could include withdrawing the catheter slightly and waiting, or delivering a small amount of nitroglycerin. If the vasospasm cannot be resolved, conduct the embolization only on the contralateral side of the prostate.
- Ensure that the tip of the micro catheter is at or inside the ostium of the prostate arteries with additional angiography.
- Procedural endpoint is stasis of the terminal branches of the arteries feeding the prostate, while maintaining patency of the main artery branches.

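### The only efficacy population leaves out PAE-arm men whose angiography rules out embolization, while controls face no matching filter; an all-attempted set should be reported beside it.

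*Combined protocol and SAP*

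**What the plan says.** Section 9.3 defines a single analysis set, which it names the Safety Population: "All PAE patients who are treated with PAE and RALRP, and all Control patients who are treated with RALRP will be included". Its next sentence reads: "This will be the population used for both safety and efficacy analyses". No all-enrolled or all-attempted set is defined anywhere.

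Appendix C places the anatomical check inside the PAE procedure: "Conduct pelvic angiography with a 5Fr catheter to evaluate aortoiliac vessels and prostate arteries during the arterial and late phases". Two of its rules can then end without any embolization. For adverse vessels or flow: "If these conditions are present on both sides of the prostate, do not embolize". For anastomoses or collaterals: "If anastomosis or endangering collateral vessels affect both sides of the prostate, no embolization will be performed". Where only one side is affected, the other side is embolized.

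Controls are chosen under section 4.2 by risk group alone ("Because we are matching PAE and control patients based on AUA risk score only") and have no angiography. The vascular exclusions in section 3.2, such as "Any contraindication to embolization, including intolerance to vessel occlusion procedures, vascular anatomy/blood flow that precludes catheter placement or embolic agent injection", stand under a section headed for the PAE population and are not restated for controls. Appendix A1 schedules an eligibility assessment for PAE patients; Appendix A2 schedules only a matching assessment for controls.

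Section 9.5.1 compares mean EBL with a matched pairs t-test. Section 9.1 removes screen failures from all tables, listings and analyses.

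**The concern.** A man enters the PAE arm as a candidate for RALRP. If angiography rules out embolization on both sides, he may still have the operation. Section 5.5 schedules the recording of EBL, operating times, transfusion, margins and hospital dates for the PAE group. He was not treated with PAE, so section 9.3 keeps those outcomes out of every comparison. A control with the same arteries is never identified and stays in.

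This is a selection after enrolment, in one arm only, on a feature that may be related to surgical bleeding. Two things are at stake. The EBL difference may carry a bias of unknown sign. A reader also cannot tell from the planned tables how often the pre-operative strategy could not be delivered, which matters in a proof-of-concept study.

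**Working it through.** **Inputs.** Ten PAE patients and ten controls matched 1:1 (sections 4 and 9.2). Paired t-test (section 9.5.1). The plan gives no alpha, SD, effect size or power, so there is no figure of its own to reproduce. Assumed here: two-sided 0.05, and a non-embolization rate f of 5% to 20%. f means no embolization on either side.

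**Who is in the set, by outcome of Visit 1**

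| PAE-arm man who has RALRP | In the 9.3 set? |
|---|---|
| Embolized on both sides | Yes |
| Embolized on one side | Yes on a natural reading (treated with PAE is not defined) |
| Not embolized, still counted as enrolled | No: not treated with PAE |
| Not embolized, called a screen failure | No: removed by section 9.1 |

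The documents do not say which of the last two rows applies. He is out either way.

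**How likely is it that someone is dropped?** P(at least one of 10) = 1 − (1 − f)^10.
- f = 0.05: 1 − 0.95^10 = 40%; expected number 0.5
- f = 0.10: 1 − 0.90^10 = 65%; expected number 1
- f = 0.20: 1 − 0.80^10 = 89%; expected number 2

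**How large could the selection bias be?** Let D be the difference in mean EBL, in EBL standard deviations, between men who cannot and men who can be embolized, with no PAE effect. If the share f is the same in both arms, controls average f·D above embolizable men and the retained PAE men average 0. The null difference (PAE minus control) is then −f·D.
- For D = ±1 its size is 0.05, 0.10 and 0.20 SD at f = 0.05, 0.10 and 0.20.
- A simulation of 100,000 trials with f = 0.20 and D = 1 gave a null difference of −0.20 SD, a type I error of 6.2% and 8.0 pairs on average. With all attempted men kept, it gave 0.00 SD and 5.0%.

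The zero depends on equal shares. If the share is f_P among enrolled PAE men and f_C among controls, the bias is −f_C·D in the treated set and (f_P − f_C)·D in the all-attempted set. The fix removes the part that arises after enrolment and leaves any difference created by the section 3.2 exclusions.

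**Against what precision?** With 10 pairs the 95% confidence half-width is 2.262/√10 = 0.72 SD of the paired difference. If EBL is uncorrelated within pairs, that SD is √2 EBL SDs, and the half-width is 0.715 × 1.414 = 1.01 EBL SD.

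**If pairs are also lost.** Power at a standardized paired difference of 1.0 is 80% with 10 pairs, 75% with 9 and 68% with 8. Whether any are lost depends on the man's undefined status.

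**The case against.** The primary objective (section 2.1) is framed around men who receive PAE. The treated set answers that question, and in a non-randomized study of 10 against 10 there is no randomization to protect. This stands: the treated set should stay, and the documents give no ground for calling it the wrong primary population.

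Exclusions 3 and 20 already bar much of the anatomy for which Appendix C stops embolization, so a man found to have it at angiography arguably failed eligibility. This makes his status open, but section 9.1 then drops him as well. Controls with the same arteries remain on either reading.

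The matched test would also drop his control. That may cost a pair. It does not undo the selection, because matching ignores arterial anatomy, and the group means in section 9.5.1 would still include that control.

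Some stronger readings are tempting but not supported:
- A reader might infer that successful embolizations are compared with unselected controls. One-sided embolization counts as treated, and controls are risk-matched and must have RALRP.
- A reader might infer that the treated analysis overstates the effect by 1/(1 − f), which is 1/0.9 = 1.11 at f = 0.10 and 1/0.8 = 1.25 at f = 0.20. That is the ratio of two different estimands. It assumes that non-embolized men bleed like controls, and under that assumption dropping them causes no selection bias.
- A reader might infer that pairs will certainly be lost. If the man is a screen failure he is not one of the ten, and the no-replacement rule in section 6 covers withdrawn patients.
- A reader might infer that his data are destroyed. Unless he is a screen failure, they would appear in the listings.

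Nor do the documents suggest a high f. In the cited human experience, one of the first two men could be embolized on one side only, and the 39-patient series mentions no abandoned procedure, although it describes treated men.

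**Conclusion.** The asymmetry is in the text of section 9.3, and Appendix C makes the excluded case a foreseen one. The planned EBL result compares men who received any embolization with controls not filtered on arterial anatomy.

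The sign of the resulting bias cannot be determined from the documents. For an assumed 1 SD difference in EBL and f of 5% to 20%, it is 0.05 to 0.20 EBL SD, well inside the uncertainty of 10 pairs. If every man is embolized, the two sets coincide and nothing changes. All sizes rest on assumed values of f and D, and on the inference that a non-embolized man goes on to RALRP with his outcomes recorded; section 6 would allow his withdrawal.

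This is a cheap improvement worth making. It does not show that the primary analysis is invalid.

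**What to change.** In section 9.3, add a pre-specified second set: all PAE-arm patients taken to Visit 1 angiography who undergo RALRP, whether or not embolized, plus controls who undergo RALRP. Report EBL and the other between-arm outcomes in this set beside the treated set, which matches the stated objective.

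Also state:
- that a man not embolized at angiography is not a screen failure for this analysis, and that his Visit 4 outcomes are recorded;
- whether he counts among the ten, and that he has a matched control. Section 9.2 ties matching to treated patients, and without a partner the paired test would drop him again;
- that one-sided embolization counts as treated with PAE, if that is the intention;
- the number of men not embolized, with reasons, as a reported result.

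The cost is one definition and one extra table set, on outcomes already scheduled, plus possibly one more control for each such man if he is added to the ten. The all-attempted difference may be smaller: if non-embolized men gain nothing, it is (1 − f) times the effect in embolized men, for example 0.90 times at f = 0.10. The change does not cure the vascular differences created before enrolment or the non-randomized allocation, and the report should say so.
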